#### **6.3.2. Caffeine, Alcohol, and Tobacco**

No alcohol will be allowed at least 24 hours before each dose and throughout the duration of each CRU visit.

No tobacco smoking or use of smokeless tobacco will be permitted while subjects are resident in the CRU.

Subjects should refrain from caffeine-containing food/beverages (for example, cola, chocolate, Milo, tea, and coffee) for at least 12 hours before each dose and throughout the duration of each CRU visit.

#### **6.3.3. Activity**

Subjects will be encouraged to maintain their regular exercise; however, they should not undertake vigorous or prolonged exercise at least 3 days before admission to the CRU. After dosing, subjects should remain recumbent or sitting in the CRU.

## 6.4. Screen Failures

Individuals who do not meet the criteria for participation in this study (screen failure) may not be rescreened.

## 7. Treatment

### 7.1. Treatment Administered

LY3185643 and rGlucagon will be supplied by Lilly or its representative in accordance with current good manufacturing practices and will be supplied with lot numbers.

Each vial of investigational product will contain 1 mg/mL of LY3185643 or rGlucagon (Lilly USA, LLC). LY3185643 or rGlucagon may be diluted for SC administration. Additional information can be found in the pharmacy instructions including detailed instructions for the preparation of the investigational products. rGlucagon will be reconstituted from the lyophilized commercial product on the day of use and will be administered within the time limits defined in the pharmacy instructions.

[Table APCA.7.1](#) shows the treatment regimens.

**Table APCA.7.1. Investigational Product Regimens**

Product:	LY3185643	rGlucagon (recombinant glucagon)
Dose range:	10 to 200 µg	10 to 200 µg
Route of administration:	subcutaneous injection	subcutaneous injection

The investigator or designee is responsible for:

- explaining the correct use of the investigational product to the site personnel
- verifying that instructions are followed properly
- maintaining accurate records of investigational product dispensing and collection
- returning all unused medication to Lilly or its designee at the end of the study

**Note:** In some cases, sites may destroy the material if, during the investigative site selection, the evaluator has verified and documented that the site has appropriate facilities and written procedures to dispose of clinical trial materials.

Subjects will be instructed to contact the investigator as soon as possible if he or she has a complaint or problem with the investigational product so that the situation can be assessed.

Study treatment will be drawn up into a 0.3-mL insulin syringe with a 6-mm/31 G needle to ensure all injections are delivered to a consistent depth target into the SC space. Each syringe will be labelled appropriately and dispensed to qualified site personnel for administration.

The doses will be administered SC in the CRU by qualified site personnel (as designated by the investigator). Injection sites selected should be approximately 5 cm from the umbilicus and the treatment administered SC with the needle applied at approximately 90 degrees without pinching the skinfold. Each injection in a given study period will be administered into a different quadrant of the anterior abdominal wall (that is, left upper quadrant, left lower quadrant, and right upper quadrant) and the site of injection for each dose will be recorded. As far as it is

practical, the same staff will administer the injections. Please refer to the pharmacy binder for detailed instructions.

### **7.1.1. *Packaging and Labeling***

LY3185643 will be packaged by Lilly or its representative in a 2-mL vial.

rGlucagon will be packaged by Lilly or its representative in a 1-mL vial.

These clinical trial materials will be labeled in accordance with local regulatory requirements.

## **7.2. *Method of Treatment Assignment***

Randomization tables with treatment codes for allocation of LY3185643 or rGlucagon will be prepared by the statistician for the study and provided to the site pharmacists involved in dose preparation. The pharmacist will provide treatment to the blinded site staff who will administer the study drugs.

### **7.2.1. *Selection and Timing of Doses***

The doses will be administered in the CRU during the treatment period on Day 1 only. The actual time of all dose administrations will be recorded in the subject's case report form (CRF).

## **7.3. *Blinding***

This study is subject- and investigator-blind. Blinding will be maintained throughout the conduct of the trial until all data are cleaned to an acceptable level of quality and locked.

Emergency codes will be available to the investigator. A code, which reveals the treatment group for a specific study subject, may be opened during the study only if the subject's well-being requires knowledge of the subject's treatment assignment.

If a subject's study treatment assignment is unblinded, the subject must be discontinued from the study unless the investigator obtains specific approval from a Lilly clinical pharmacologist or clinical research physician (CRP) for the study participant to continue in the study. During the study, emergency unblinding should occur only by accessing the study subject's emergency code.

In case of an emergency, the investigator has the sole responsibility for determining if unblinding of a subject's treatment assignment is warranted for medical management of the event. Subject's safety must always be the first consideration in making such a determination. If the investigator decides that unblinding is warranted, the investigator should make every effort to contact the Lilly clinical pharmacologist or CRP before unblinding a study subject's treatment assignment unless this could delay emergency treatment of the subject. If a study subject's treatment assignment is unblinded, Lilly must be notified immediately.

Upon completion of the study, all codes must be returned to Lilly or its designee.

## **7.4. *Dose Modification***

There will be no dose modifications of LY3185643 and rGlucagon.

## **7.5. Preparation/Handling/Storage/Accountability**

All clinical trial material provided to the investigator will be stored in a secure place and allocated and dispensed by appropriately trained persons. The allocation and dispensing of the investigational products will be fully documented and verified by a second person. Detailed records of the amounts of the investigational product received, dispensed, and remaining at the end of the study will be maintained.

Only participants enrolled in the study may receive investigational product and only authorized site staff may supply or administer study treatment. All study treatments should be stored in an environmentally controlled and monitored (manual or automated) area in accordance with the labeled storage conditions with access limited to the investigator and authorized site staff.

The investigator is responsible for study treatment accountability, reconciliation, and record maintenance (such as receipt, reconciliation and final disposition records). The investigator site will be permitted to destroy the investigational material after written approval is obtained from the sponsor.

## **7.6. Treatment Compliance**

Every attempt will be made to select subjects who have the ability to understand and comply with instructions. Noncompliant subjects may be discontinued from the study.

The investigational product will be administered at the CRU and documentation of treatment administration will occur at the site.

The specifications in this protocol for the timings of safety, PK, and PD sampling are given as targets to be achieved within reasonable limits. Modifications may be made to the time points based upon the safety and PK information obtained. The scheduled time points may be subject to minor alterations; however, the actual time must be correctly recorded in the CRF. Failure to obtain samples due to clinical issues, such as problems with venous access, technical difficulty with obtaining samples, or subject no show for planned procedural visits will not be considered a protocol deviation but the site will still be required to notify the sponsor in writing.

Any major modifications that might affect the conduct of the study, subject safety, and/or data integrity will be detailed in a protocol amendment.

## **7.7. Concomitant Therapy**

Subjects should not use over-the-counter or prescription medication within 7 and 14 days, respectively, before each dosing (apart from vitamin/mineral supplements, occasional paracetamol, hormone replacement therapy, or thyroid-replacement therapy).

If the need for concomitant medication arises, inclusion or continuation of the subject may be at the discretion of the investigator and, if possible, after consultation with a Lilly clinical pharmacologist or CRP. Any additional medication used during the course of the study must be documented.

## **7.8. Treatment after the End of the Study**

LY3185643 and rGlucagon will not be made available to subjects after conclusion of the study.

## 8. Discontinuation Criteria

### 8.1. Discontinuation from Study Treatment

Discontinuation of the investigational product for abnormal liver tests **should be considered** by the investigator when a subject meets one of the following conditions after consultation with the Lilly designated medical monitor:

- alanine aminotransferase (ALT) or aspartate aminotransferase (AST)  $>5X$  upper limit of normal (ULN)
- ALT or AST  $>3X$  ULN along with one of the following criteria
  - sustained for more than 2 weeks or
  - total bilirubin level  $>2X$  ULN or
  - prothrombin time  $>1.5X$  ULN or
  - appearance of fatigue, nausea, vomiting, right upper-quadrant pain or tenderness, fever, rash, and/or eosinophilia ( $>5\%$ )
- alkaline phosphatase (ALP)  $>3X$  ULN
- ALP  $>2.5X$  ULN and total bilirubin level  $>2X$  ULN
- ALP  $>2.5X$  ULN with the appearance of fatigue, nausea, vomiting, right quadrant pain or tenderness, fever, rash, and/or eosinophilia ( $>5\%$ )

Subjects who discontinue the investigational product early will have procedures performed as shown in the Schedule of Activities (Section 2).

#### 8.1.1. Discontinuation of Inadvertently Enrolled Subjects

If the sponsor or investigator identifies a subject who did not meet enrollment criteria and was inadvertently enrolled, a discussion must occur between the Lilly clinical pharmacologist/CRP and the investigator to determine if the subject may continue in the study. If both agree it is medically appropriate to continue, the investigator must obtain documented approval from the Lilly clinical pharmacologist/CRP to allow the inadvertently enrolled subject to continue in the study with or without continued treatment with investigational product.

### 8.2. Discontinuation from the Study

Subjects will be discontinued in the following circumstances:

- enrollment in any other clinical trial involving an investigational product or enrollment in any other type of medical research judged not to be scientifically or medically compatible with this study
- participation in the study needs to be stopped for medical, safety, regulatory, or other reasons consistent with applicable laws, regulations, and good clinical practice (GCP)

- investigator decision
  - the investigator decides that the subject should be discontinued from the study
- subject decision
  - the subject, or designee (for example, parents or legal guardian) requests to be withdrawn from the study

Subjects who discontinue the study early will have end-of-study procedures performed as shown in the Schedule of Activities (Section 2).

### **8.3. Subjects Lost to Follow-Up**

A subject will be considered lost to follow-up if he or she repeatedly fails to return for scheduled visits and is unable to be contacted by the study site. Site personnel are expected to make diligent attempts to contact subjects who fail to return for a scheduled visit or were otherwise unable to be followed up by the site.

## 9. Study Assessments and Procedures

Section 2 lists the Schedule of Activities, detailing the study procedures and their timing (including tolerance limits for timing).

[Appendix 2](#) lists the laboratory tests that will be performed for this study.

[Appendix 5](#) provides a summary of the maximum number and volume of invasive samples for all sampling during the study.

Unless otherwise stated in subsections below, all samples collected for specified laboratory tests will be destroyed within 60 days of receipt of confirmed test results. Certain samples may be retained for a longer period, if necessary, to comply with applicable laws, regulations, or laboratory certification standards.

Investigators must document their review of each laboratory safety report.

### 9.1. Efficacy Assessments

This section is not applicable for this study.

### 9.2. Adverse Events

Investigators are responsible for monitoring the safety of subjects who have entered this study and for alerting Lilly or its designee to any event that seems unusual, even if this event may be considered an unanticipated benefit to the subject.

The investigator is responsible for the appropriate medical care of subjects during the study.

The investigator remains responsible for following, through an appropriate health care option, AEs that are serious or otherwise medically important, considered related to the investigational product or the study, or that caused the subject to discontinue the investigational product before completing the study. The subject should be followed until the event resolves, stabilizes with appropriate diagnostic evaluation, or is reasonably explained. The frequency of follow-up evaluations of the AE is left to the discretion of the investigator.

After the informed consent form (ICF) is signed, study site personnel will record, via CRF, the occurrence and nature of each subject's preexisting conditions, including clinically significant signs and symptoms of the disease under treatment in the study. Additionally, site personnel will record any change in the condition(s) and the occurrence and nature of any AEs.

The investigator will interpret and document whether or not an AE has a reasonable possibility of being related to study treatment or a study procedure, taking into account the disease, concomitant treatment, or pathologies.

A "reasonable possibility" means that there is a cause and effect relationship between the investigational product and/or study procedure and the AE.

Planned surgeries should not be reported as AEs unless the underlying medical condition has worsened during the course of the study.

If a subject's investigational product is discontinued as a result of an AE, study site personnel must report this to Lilly or its designee via CRF.

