### **9.2.1. Serious Adverse Events**

An SAE is any AE from this study that results in one of the following:

- death
- initial or prolonged inpatient hospitalization
- a life-threatening experience (that is, immediate risk of dying)
- persistent or significant disability/incapacity
- congenital anomaly/birth defect
- events considered significant by the investigator based upon appropriate medical judgment

Study site personnel must alert Lilly, or its designee, of any SAE within 24 hours of investigator awareness of the event via a sponsor-approved method. If alerts are issued via telephone, they are to be immediately followed with official notification on study-specific SAE forms. This 24-hour notification requirement refers to the initial SAE information and all follow-up SAE information.

Although all AEs are recorded in the CRF after signing informed consent, SAE reporting begins after the subject has signed informed consent and has received investigational product.

However, if an SAE occurs after signing informed consent, but before receiving investigational product, AND is considered reasonably possibly related to a study procedure then it MUST be reported.

Investigators are not obligated to actively seek AEs or SAEs in subjects once they have discontinued from and/or completed the study (the subject summary CRF has been completed). However, if the investigator learns of any SAE, including a death, at any time after a subject has been discharged from the study and he/she considers the event reasonably possibly related to the study treatment or study participation, the investigator must promptly notify Lilly.

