#### 10.3.1. Safety Analyses

##### 10.3.1.1. Clinical Evaluation of Safety

All investigational product and protocol procedure AEs will be listed, and if the frequency of events allows, safety data will be summarized using descriptive methodology.

The incidence of symptoms for each treatment will be presented by severity and by association with investigational product as perceived by the investigator. Symptoms reported to occur before first dose will be distinguished from those reported as new or increased in severity during the study. Each symptom will be classified by the most suitable term from the medical regulatory dictionary.

The number of investigational product-related SAEs will be reported.

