9.5 Safety and Tolerability Assessments

9.5.1 Adverse events

Where changes in severity are recorded in the Case Report Form (CRF), each separate severity of the AE will be reported in the listings, only the most severe will be used in the summary tables. A pre-existing condition is defined as an AE that starts before the subject has provided written informed consent and is ongoing at consent. A non-treatment emergent AE is defined as an AE which starts after informed consent but prior to dosing. A treatment-emergent AE is defined as an AE which occurs postdose or which is present prior to dosing and becomes more severe postdose.

All AEs will be listed. Treatment-emergent AEs will be summarized by treatment, severity and relationship to the study drug. The frequency (the number of AEs, the number of subjects experiencing an AE and the percentage of subjects experiencing an AE) of treatment-emergent AEs will be summarized by treatment, Medical Dictionary for Regulatory Activities (MedDRA) version 19.0 system organ class and preferred term. The summary and frequency AE tables will be presented for all causalities and those considered related to the study drug. Any serious AEs will be tabulated.

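### Protocol section 9.2 defines a reasonable possibility of relatedness as actual causation; taken literally, suspected but unestablished events would count as not related

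*Protocol*

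**What the plan says.** For each AE, Protocol section 9.2 has the investigator document "whether or not an AE has a reasonable possibility of being related to study treatment or a study procedure". The next sentence defines the key phrase: a reasonable possibility "means that there is a cause and effect relationship between the investigational product and/or study procedure and the AE". The definition contains no qualifier such as may or suggests. Neither document gives an intermediate category or a second causality scale.

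The call is then used in these places:

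- **Protocol 9.2.1, before dosing.** The protocol covers an SAE that occurs after consent but before any investigational product is given, "AND is considered reasonably possibly related to a study procedure then it MUST be reported".
- **Protocol 9.2.1, after discharge from the study.** If the investigator learns of an SAE and "he/she considers the event reasonably possibly related to the study treatment or study participation, the investigator must promptly notify Lilly".
- **Protocol 9.2.1.1.** A serious event that is absent from the IB is a SUSAR when the investigator identifies it as related to product or procedure.
- **Protocol 10.3.1.1.** Symptoms are presented "by association with investigational product as perceived by the investigator". The section adds: "The number of investigational product-related SAEs will be reported".
- **SAP 9.5.1.** "The summary and frequency AE tables will be presented for all causalities and those considered related to the study drug".

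**The concern.** A possibility of causation and the existence of causation are different thresholds. The request in 9.2 uses the first and the definition substitutes the second. An investigator who thinks a drug effect plausible but cannot say that it occurred should answer yes to the request and no to the definition.

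Adverse events are the only endpoint listed for the secondary objective (Protocol section 4). If some calls follow the definition and others the ordinary sense of the phrase, the related-event tables have no single meaning. If the definition is followed throughout, they understate suspected drug effects. A few SAE duties that depend on the same call would then also have a higher threshold than their own wording conveys.

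**Working it through.** There is no figure to reproduce. The check is textual: follow the definition to each place where relatedness decides something, and look for wording that overrides it.

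**Step 1: does anything correct the definition?** No. The sentence is current protocol text. The glossary in Appendix 1 defines an AE but not relatedness. SAP 9.5.1 refers to events considered related to study drug without defining related. Other wording points the opposite way. Section 9.2.1 speaks of events reasonably possibly related. Section 9.2.1.1 is built on suspicion. Section 9.4.6 allows extra samples where an immunological cause is merely possible.

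**Step 2: what happens to an event that is suspected but not established as causal?** The record is yes or no. Under the definition the answer is no, so in effect the event is recorded as not related.

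**Step 3: what depends on that record?**

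| Item | Source | Depends on relatedness? |
|---|---|---|
| Reporting of a pre-dose SAE | Protocol 9.2.1 | Yes |
| Notification of an SAE learned of after discharge | Protocol 9.2.1 | Yes |
| SUSAR identification | Protocol 9.2.1.1 | Yes |
| Presentation of symptoms by association | Protocol 10.3.1.1 | Yes |
| Count of product-related SAEs | Protocol 10.3.1.1 | Yes |
| Related-AE tables | SAP 9.5.1 | Yes |
| Follow-up of AEs that are not serious, not medically important and did not end treatment | Protocol 9.2 | Yes |
| 24-hour alert for any SAE once product has been received | Protocol 9.2.1 | No |
| Follow-up of serious or medically important AEs, and of AEs that ended treatment | Protocol 9.2 | No |
| Listing of all AEs, all-causality tables, tabulation of serious AEs | SAP 9.5.1 | No |

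**Result.** Three SAE duties, three outputs and one residual follow-up duty depend on the call. The main SAE alert and the complete AE record do not.

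**The case against.** The strongest reply is that this is loose drafting with little effect. The operative instruction asks for a judgement of possibility, and 10.3.1.1 reports association as the investigator perceives it. An experienced investigator may simply apply the ordinary meaning. The endpoint is adverse events, not related ones, and the full AE record is kept whatever the call. The post-discharge gap is narrow: the follow-up or early-termination visit is at least 30 days after the last dose (Schedule of Activities), and the half-life of LY3185643 is under 1 hour (9.4.6). Section 9.2 also has a general duty to tell the sponsor of anything unusual.

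Most of this stands, and it limits the impact. It does not remove the fault, because the protocol should not depend on its own definition being ignored. The general duty is also not a substitute for an SAE reporting trigger.

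A reader might infer more than the documents support:

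- **That suspected events must be recorded as unrelated.** Neither document says so. It is the effect of applying the definition literally.
- **That blinding prevents attribution.** Every injection is LY3185643 or rGlucagon, both supplied as investigational products, and there is no placebo. Blinding hides which product and dose was given, not that one was given. Deciding which of three same-day injections was responsible is a separate problem.
- **That serious events during the study would go unreported.** Once dosing has started, the 24-hour alert covers any SAE.
- **That half of the AE tables are affected.** The table list is in the TFL shell document, which is not available here.
- **That the earlier study sizes the undercount.** Protocol 3.2.1 gives 10 + 6 + 3 + 3 + 2 = 24 of 36 events (67%) as nausea, vomiting, headache, dizziness or light-headedness. It gives no causality calls and no definition of relatedness, so these counts say nothing about how many would change category.

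**Conclusion.** The point holds as a wrong rule in the text, with limited reach. Section 9.2 equates a reasonable possibility with established causation. That contradicts the term itself and conflicts with 9.2.1 and 9.2.1.1. Followed as written, it takes suspected events out of the related-AE tables and the product-related SAE count. It also raises the threshold for SUSAR identification and for the pre-dose and post-discharge SAE triggers.

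The size of any undercount cannot be estimated from the documents. The conclusion assumes that the definition is applied literally and that the CRF, which is not among the documents, records the same yes/no call without a corrective definition. If investigators use the ordinary meaning, the counts do not change, but the inconsistency between the sections remains.

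**What to change.** Reconcile 9.2, 9.2.1 and 9.2.1.1 by replacing the defining sentence with wording such as: *A reasonable possibility means that there are facts or arguments that suggest a causal relationship; the relationship need not be established.* Put the same wording in the CRF completion guide, and state in SAP 9.5.1 that related has this meaning, so that the related-AE tables and the SAE count in Protocol 10.3.1.1 rest on one definition.

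Appendix 6 refers to drop-outs among early participants, so some calls may already have been recorded. These should be confirmed against the new wording before database lock, while the investigator is still blinded.

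The cost is one protocol sentence, a matching line in the CRF guide and the SAP, and a check of calls already made. The design, sample size and PK/PD models do not change. The downside is a possibly higher count of related events.
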